### **Serious Adverse Event**

An adverse event that:

- is life threatening;
- results in permanent impairment of a body function;
- results in permanent damage to a body structure;
- necessitates medical or surgical intervention to preclude permanent impairment of a body function or permanent damage to a body structure; or
- results in hospitalization or prolongation of hospitalization.

### **Seroma**

A fluid collection in a tissue location.

### **Surgical Site Infection**

Erythema at the surgical incision in conjunction with a fever or an elevated white blood cell count.

## **9. RISK ANALYSIS**

### **9.1. General Risks Associated with Surgery**

The risks associated with surgery are described to subjects in the surgical consent form. Those potential complications are the following:

- Bleeding episodes during or after the procedure, in severe cases blood transfusion may be necessary;
- Swelling after the procedure;
- Pain after the procedure;
- Nerve damage causing numbness, tingling, pain and/or weakness in the affected area;
- Local or systemic allergic reactions to medications, surgical instruments, sutures and/or topical preparations used for the procedure;
- Venous or arterial thrombosis possibly leading to myocardial infarction, cerebrovascular accident or pulmonary embolism; and
- Complications from general anesthesia or surgery, which though very rare, could cause death.

### **9.2. Risks Associated with Tissue Expanders**

The risks associated with tissue expanders during breast reconstruction are described to subjects in the surgical consent form provided separately by the surgeon. The risks associated with tissue expanders are:

- Deflation;
- Tissue damage;
- Infection;

- Extrusion;
- Hematoma;
- Seroma;
- Capsular contracture;
- Premature explantation;
- Displacement;
- Compression on the bones of the chest wall;
- Pain;
- Dysesthesia (abnormal sensation);
- Distortion;
- Inadequate tissue flap; and
- Inflammatory reaction.

The occurrence of one or more of the above complications may require medical or surgical treatment, including additional surgery or tissue expander removal.

### **9.3. Risks Associated with Breast Implants**

The risks associated with breast implants are described to subjects in the surgical consent form provided separately by the surgeon. Those complications that occur in  $\geq 1\%$  of patients receiving breast implants are as follows:

- Asymmetry;
- Breast feeding difficulties;
- Breast pain;
- Ptosis;
- Calcification;
- Capsular contracture;
- Chest wall deformity;
- Deflation of the breast implant;
- Delayed wound healing;
- Extrusion;
- Hematoma;
- Iatrogenic injury or damage;
- Implant displacement or malposition;
- Implant palpability;
- Implant visibility;
- Implant wrinkling or rippling;
- Infection;
- Inflammation or irritation;
- Necrosis;
- Nipple or breast changes, including change in or loss of nipple sensation;
- Redness or bruising;
- Rupture of the breast implant;
- Scarring;
- Seroma;
- Skin rash;
- Lymphedema or lymphadenopathy;
- Breast tissue atrophy; and
- Unsatisfactory appearance due to implant style or size.

The occurrence of one or more of the above complications may require medical or surgical treatment, including additional surgery or implant removal.

#### **9.4. Risks Associated with Biologic Surgical Mesh**

The potential risks and benefits of participation in this trial are described in the subject informed consent form and are to be explained to the subject and/or their legal representative prior to participating in the trial.

The potential complications associated with the use of biologic surgical mesh during breast reconstruction are listed below. These complications are therefore also possible with the use of Meso BioMatrix during breast reconstruction. However, there may be unforeseen additional risks. The potential investigational device related complications are:

- Infection;
- Seroma;
- Hematoma;
- Tissue necrosis;
- Dehiscence;
- Erythema;
- Local or systemic allergic reaction to the Meso BioMatrix implant; and
- Defect Recurrence.

#### **9.5. Risk Associated with Tissue Biopsy**

During the second stage surgery, Investigators will obtain a total of four small biopsies: One at the Meso BioMatrix implant superior interface, one in the center of the Meso BioMatrix implant, one at the Meso BioMatrix implant inferior interface and one posterior to the expander. The risks associated with these tissue biopsies during the second stage surgery are:

- Infection at the biopsy location
- Bleeding at the biopsy location
- Weakening of the tissue surrounding the biopsy location

#### **9.6. Risk Mitigation**

In order to reduce the risk of potential adverse events to subjects recruited for this trial, subjects with higher surgical risk factors and known confounding risk factors have been excluded. In addition, subject subgroups that are known to have a reduced chance of a successful outcome (i.e. smokers, subjects undergoing peri-operative radiation therapy, obesity, etc.) due to confounding risk factors have been excluded from the trial.

Formal trial stopping rules have been defined in section 11.4.1 to assist with limiting exposure to the investigational device should known serious adverse events occur at a higher than expected rate or potentially unforeseen risks occur in study subjects.

It is expected that the investigational device implantation procedure will not add any significant additional operative time compared to the procedure as it is normally performed with AlloDerm or autologous tissue. In addition, the study required antibiotic regimens are consistent with the study investigators' standard of care.

Taking biopsies from the surgical mesh during the second stage surgery may increase certain risks. However, subjects will take prophylactic antibiotics to mitigate the risk of infection. Further, in the case of bleeding, surgeons can observe the biopsy sites during the second stage of the reconstruction and can address bleeding appropriately. Lastly, the biopsy specimens will be quite small relative to the surface area of the surgical mesh. Therefore, weakening of the mesh after biopsy is unlikely.

The Meso BioMatrix was designed and developed according to the Quality System Regulation. Device sterilization has been validated. Numerous in vivo animal studies have been conducted

with the Meso BioMatrix that demonstrated the biocompatibility, safety and effectiveness of the implant for soft tissue repair and reinforcement.

#### **9.7. Anticipated Clinical Benefits**

As described in the scientific literature, a majority of subjects who undergo tissue-expander assisted breast reconstruction with biologic surgical mesh experience improved aesthetic outcomes compared to tissue-expander assisted reconstruction without biologic surgical mesh or mastectomy alone. Therefore, it is expected that the majority of subjects in this trial will also experience satisfactory aesthetic outcomes. In addition, as reported in the AlloDerm literature, patients may experience less post-operative pain, reduced time to full expansion, reduced time between the first and second stage of the breast reconstruction and less capsular contracture as compared to two-stage, tissue-expander assisted reconstruction without a surgical mesh. The information gained from the conduct of this trial may be of benefit to other people with the same medical condition.

#### **9.8. Alternative Treatments**

Subjects do not have to participate in this trial to receive breast reconstruction surgery. There are alternative surgical methods available including direct to implant breast reconstruction, tissue expander-assisted implant reconstruction with an alternative biologic surgical mesh (albeit off-label), expander-assisted implant reconstruction without a biologic surgical mesh, and autologous flap reconstruction. These procedures each have different risk and benefit profiles. Subjects are informed about these alternative procedures in the informed consent form and are encouraged to discuss them with the Investigators.

### **10. TRIAL DATA COLLECTION, MONITORING AND QUALITY MANAGEMENT**

#### **10.1. Data Management**

##### *10.1.1. Clinical Trial Database*

The clinical trial database will be compliant with Part 11 of Title 21 of the United States Code of Federal Regulations. Data type, range and logic verification edit checks will be programmed into the database.

##### *10.1.2. Case Report Form*

Clinical trial data were originally recorded on paper-based case report forms. Those case report forms were printed on 3-part NCR paper and provided in single patient binders. In the spring of 2014, the case report forms will become electronic for the remainder of the trial. The electronic case report form is eClinical OS™ (Merge Healthcare Incorporated located in Morrisville, NC).

##### *10.1.3. Data Entry and Quality Control*

Each field on the case report form will be entered into the clinical trial database. Each field will be subjected to data type verification and range checking, as appropriate. After a case report form page is entered into the database, a second staff member then compares the entered data to the case report form in order to identify discrepancies between the case report form and the clinical database. Any identified discrepancies are resolved within the database and the reason for data change is recorded in the data audit trail.

##### *10.1.4. Data Cleaning and Editing*

Periodic analysis of each data field across all entered subjects will be performed in order to identify omitted data, data discrepancies and outliers for possible data mistakes. Any discovered errors are then referred to the clinical site Research Coordinator or Investigator as a query on a data clarification form. The Research Coordinator or Investigator will review and respond to the query(s) on the data clarification form. Corrected data is entered in the clinical database and the reason for data change is recorded in the data audit trail.

#### *10.1.5. Data Storage*

The clinical trial database will reside on a secure server that will be backed up on a regular basis. Case report forms and data clarification forms will be stored in a secure storage room.

#### *10.1.6. Trial Data Retention*

Clinical trial data will be maintained by DSM Biomedical for no less than two years after the completion or termination of the trial or no less than two years after marketing application approval for the investigational device, whichever event occurs the latest. Clinical sites will be required to adhere to the same trial data retention period.

### **10.2. Clinical Site Initiation**

When a site has fulfilled all relevant regulatory (i.e., FDA approval and IRB approval) and sponsor requirements (i.e., execution of a Clinical Research Trial Agreement, submission of required regulatory documents), a site initiation visit will be conducted. At the site initiation visit, the clinical site's Principal Investigator and Research Coordinator will receive training on the Investigational Plan and trial procedures.

### **10.3. Trial Data Monitoring**

In order to assess the completeness and accuracy of the data provided by each site, the monitor will perform 100% source document verification of data in the case report form for each subject in the trial. The monitor will notify the Research Coordinator and/or Investigator of any data discrepancies between the source medical records and the case report form found during monitoring. When all fields on an individual case report form page have been verified, the monitor will initial and date the "Source Document Verification" box at the bottom of the page. The top two copies of each case report form page will be removed and submitted to data management.

### **10.4. Clinical Site Closeout**

When all clinical data from each clinical site have been monitored and cleaned, a site closeout will be conducted. At the closeout, the monitor will verify that clinical data for all subjects are present and all required regulatory documents are present and up to date. Lastly, the monitor will ensure that the clinical site understands their trial data retention responsibilities.

## **11. STATISTICAL CONSIDERATIONS**

### **11.1. Sample Size Justification**

This is a feasibility trial with no formal statistical hypothesis. Therefore, the sample size of 25 subjects was empirically chosen.

### **11.2. Statistical Analysis**

#### *11.2.1. Data Presentation*

All clinically relevant demographic, baseline, procedure and outcome variables will be summarized by scheduled visit using frequency tables and descriptive statistics as appropriate in accordance with sections 8.2, 8.3, 8.4, 8.7 and 8.8 of the Guidance for Industry and FDA Staff – Saline, Silicone Gel and Alternative Breast Implants.

#### **11.3. Interim Analysis Plans**

There will be no interim analysis.

#### **11.4. Criteria for Trial Termination**

All serious adverse events and unanticipated adverse device effects reported during the trial will be evaluated to determine if the investigational device poses an unacceptable risk to subjects. If an unacceptable risk is determined in the judgment of the Investigators, the sponsor and/or the U.S. Food & Drug Administration, enrollment in the trial will be suspended while an

investigation into the cause of the unacceptable risk is undertaken. If the unacceptable risk cannot be mitigated by modifications to the investigational device or the investigational plan, the trial will be terminated.

#### *11.4.1. Stopping Rules Related to the Investigational Device*

DSM Biomedical will follow the below formal stopping rules in order to assure that enrollment will be suspended in a timely manner should potential serious safety issues arise unique to the investigational device:

- A serious immune reaction requiring surgical revision/removal of the investigational device occurs in 2 subjects.
- An investigational device malfunction requiring post-operative surgical revision/removal of the investigational device occurs in 3 subjects.
- A serious adverse event potentially related to the investigational device occurs in 5 subjects.
- A serious unanticipated adverse device effect is determined to have occurred.

Should one of the above stopping criteria occur, DSM Biomedical shall suspend enrollment as soon as possible, but not later than 5 working days after the determination that a stopping rule criterion has been met. The trial will remain suspended until the FDA and the each IRB have approved trial resumption.

#### *11.4.2. Success Criteria*

The purpose of this study is to demonstrate the safety and feasibility of the use of the Meso BioMatrix device when used for two-stage, tissue-expander assisted breast reconstruction. In order to warrant further study of the use of Meso BioMatrix device during breast reconstruction, the complications seen in this study should not be significantly greater than the complications seen in the AlloDerm literature. As described in the three recent systematic literature reviews cited in section 4.2 of this protocol, the rates of individual breast related adverse events associated with the use of AlloDerm are variable and, due to the retrospective nature of many of the articles in the AlloDerm literature, are likely underreported. Nonetheless, the AlloDerm literature provides a basis for assessing the initial safety of the Meso BioMatrix device. Based on the AlloDerm literature (reference section 4.2), the below rates of individual Meso BioMatrix related adverse events will be considered clinically acceptable for this pilot phase trial and may support progression to a pivotal phase trial:

- 0% rate of death,
- 0% rate of anaphylaxis,
- $\leq 8\%$  rate of severe acute inflammatory response,
- $\leq 12\%$  rate of infection,
- $\leq 20\%$  rate of flap necrosis,
- $\leq 10\%$  rate of Baker Grade 4 capsular contracture in breasts that do not receive post-operative radiation therapy.

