#### 4.2.

#### Relevant Systematic Literature Reviews

Three recent systematic literature review articles were published regarding the use of acellular dermal matrices (“ADM”) during breast reconstruction. Jansen et al. tabulated adverse events from 14 relevant articles presenting outcomes after use of AlloDerm^16. Newman et al. tabulated adverse events from 12 relevant articles reporting outcomes after use of AlloDerm. It should be noted that 3 of those 12 articles included 3 other biologic mesh devices along with AlloDerm^17. Hoppe et al. tabulated adverse events from 7 relevant articles comparing outcomes with and without the use of AlloDerm during breast reconstruction. The adverse events tabulated in their systematic reviews are compared in Table 1.

Table 1: Adverse Events Listed Systematic Review Articles for Breast Reconstruction

Adverse Event Term	Jansen et al.* (AlloDerm only)	Newman et al. (ADM)	Hoppe et al. (AlloDerm only)
Breast Reconstruction	# of Implants = 655	# of Implants = 789	# of Implants = 977
Infection	0 - 11%	5.2%	7.6%
Seroma	0 - 9%	6.0%	9.4%
Necrosis	0 - 25%	9.4%	Not reported
Hematoma	0 - 6.7%	Not reported	1.4%
Exposure w/ Prosthesis Loss	0 - 14%	Not reported	Not reported
Exposure w/ Prosthesis Salvage	0 - 4%	Not reported	Not reported
Capsular Contracture	0 - 8%	Not reported	Not reported

\* Only probability ranges were presented due to limitations in underlying data

Jansen et al. and Hoppe et al. compared the rates of AlloDerm associated adverse events to adverse events in breast reconstruction without a biologic mesh. Jansen et al. found comparable rates of adverse events when a biologic mesh is used for breast surgery versus no biologic mesh use. However, Hoppe et al. found higher rates of adverse events when AlloDerm is used, but concluded that AlloDerm use may lead to greater patient satisfaction. It is important to note that the majority of articles in the above systematic review articles were retrospective, single-center

experiences. Such articles are prone to bias since adverse events are usually not uniformly defined and documented. Therefore, the true incidence of complications may have been underreported in the studies included in the above systematic reviews.

The potential benefits to AlloDerm assisted breast reconstruction cited in these systematic review articles are:

- Increased initial tissue expander fill volume
- Reduced operative time

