### Breast-related Adverse Events

Any untoward medical occurrence related to the reconstructed breast. Adverse events that meet this definition include but are not necessarily limited to:

- Infection
- Seroma
- Hematoma
- Tissue necrosis
- Dehiscence
- Red breast syndrome
- Allergic reaction
- Inflammatory response
- Meso BioMatrix failure
- Prosthesis extrusion
- Prosthesis (tissue expander or implant) failure
- Capsular contracture (grade 2-4)

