### Capsular Contracture

Defined as tightening of the tissue capsule around a breast implant. Capsular contracture is categorized according to the Baker capsular contracture grading system below:

- Grade I = Breast is normally soft and looks natural
- Grade II = Breast is a little firm but looks normal
- Grade III = Breast is firm and looks abnormal
- Grade IV = Breast is hard, painful, and looks abnormal

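### The contracture success limit in 11.4.2 counts Baker Grade 4 only, so it does not measure the AlloDerm figure it is said to rest on, and a device with more contracture than that figure can meet it

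*Combined protocol and SAP*

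**What the plan says.** Section 11.4.2 (Success Criteria) gives the aim that "the complications seen in this study should not be significantly greater than the complications seen in the AlloDerm literature". It then states: "Based on the AlloDerm literature (reference section 4.2), the below rates of individual Meso BioMatrix related adverse events will be considered clinically acceptable". One of the six limits that follow is a rate of at most 10% for the "rate of Baker Grade 4 capsular contracture in breasts that do not receive post-operative radiation therapy".

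Section 4.2, Table 1, is the cited basis. Its contracture row reads "Capsular Contracture 0 - 8" (percent) for one of the three systematic reviews, and the other two did not report contracture. A footnote to that review's column says "Only probability ranges were presented due to limitations in underlying data". The table shows no Baker grade and no radiation restriction for this row.

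Section 8 (Trial Definitions) counts capsular contracture of grades 2 to 4 as a breast-related adverse event, and so towards the primary endpoint. It also defines the grades: "Grade III = Breast is firm and looks abnormal". Grade IV adds hardness and pain.

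**The concern.** A limit said to come from a literature figure should count the same event as that figure. This one counts only the most severe of the four Baker grades, whereas the source row is labelled simply "Capsular Contracture". A Grade III breast, firm and abnormal-looking, meets the primary endpoint but cannot count against the contracture limit.

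The limit is one of six that section 11.4.2 uses to judge whether a pivotal trial may be supported. If it is met while Grade II or III contracture is common, the result could be read as contracture in line with the AlloDerm literature when it is not.

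**Working it through.** **No figure to reproduce.** The documents give no derivation of the 10% limit, and section 11.1 states that there is no formal hypothesis and that 25 subjects were chosen empirically. The check is therefore a comparison with the cited source, followed by the probability of meeting the limit.

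**1. Limit against source.**

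| | Table 1 figure | 11.4.2 limit | Trial's adverse event definition (section 8) |
|---|---|---|---|
| Grades counted | none stated | 4 only | 2 to 4 |
| Breasts counted | no radiation restriction shown | no post-operative radiation | reconstructed breast |
| Rate | 0-8% | at most 10% | none set |

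**2. Direction.** Grade 4 is a subset of any contracture count that includes it. Whatever grades the review counted, a Grade 4 count cannot be larger than a count on the review's definition.

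**3. Counts that meet the limit.** Eligibility allows unilateral or bilateral reconstruction, so 25 subjects give 25 to 50 breasts (the bilateral share is not stated). Largest passing count = floor(ceiling × n):

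| Breasts n | 10% ceiling | 8% ceiling |
|---|---|---|
| 25 | 2 | 2 |
| 30 | 3 | 2 |
| 35 | 3 | 2 |
| 40 | 4 | 3 |
| 50 | 5 | 4 |

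At 25 breasts the two ceilings are the same rule. At 30, 35, 40 and 50 breasts, 10% admits one more event. Grades II and III are not limited at any n: contracture in 25 of 25 breasts would meet the limit if no more than 2 were Grade 4.

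**4. Probability of meeting the limit as written.** P = sum over x = 0 to c of C(n, x) p^x (1−p)^(n−x), where c is the 10% count above and p is the true Grade 4 rate. Assumptions, none of them from the documents:

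- the true contracture rate is 24%, which is 3 × the 8% top of the range;
- a quarter or a half of contractures are Grade 4, so p = 0.24 × 0.25 = 0.06 or p = 0.24 × 0.5 = 0.12;
- breasts are independent;
- every Grade 4 contracture is counted. Section 11.4.2 words its limits as device-related events, so attributing some of them elsewhere would only raise these probabilities.

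Worked case, n = 25, p = 0.06: 0.2129 + 0.3398 + 0.2602 = 0.813.

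| n | Quarter Grade 4 (p = 0.06) | Half Grade 4 (p = 0.12) | All counted grades at the same 10% ceiling (p = 0.24) |
|---|---|---|---|
| 25 | 0.813 | 0.409 | 0.041 |
| 35 | 0.844 | 0.381 | 0.019 |
| 50 | 0.922 | 0.435 | 0.011 |

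The last column keeps the 10% ceiling, so the difference between the columns is due to the grade restriction alone. Rounding of the count makes the figures uneven in n: at 30 and 40 breasts they are 0.897 and 0.910 for a quarter, and 0.507 and 0.467 for a half.

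On independence: if all 25 subjects were bilateral and both breasts always agreed, 5 of 50 breasts would mean at most 2 of 25 subjects. That returns the 25-breast figures.

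**5. Cost of a strict 8% ceiling.** If the true rate of the counted event is exactly 8%, the probability of missing an 8% ceiling is 1 − P(X ≤ c), with c from the 8% column: 0.323 (25 breasts), 0.539 (35) and 0.371 (50).

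**The case against.** The strongest reply has four parts.

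*The literature rates are probably too low.* Sections 4.2 and 11.4.2 both say that complications are likely underreported in largely retrospective articles. A prospective limit somewhat above 8% fits that reasoning, and the limits are not uniformly lenient: necrosis is capped at 20% against a literature maximum of 25%. This stands as a possible reason for a margin, although none is quantified. It does not explain leaving out Grade III.

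*Table 1 does not say which grades were counted.* This also stands. If the review counted Grade 4 only, the definitions would agree and only the 10%-versus-8% gap would remain, with no effect at 25 breasts. But the documents give no sign of this, and the trial's own definition is wider.

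*Grades II and III are not ignored elsewhere.* They enter the primary endpoint, contracture needing unplanned surgery would generally be a serious adverse event (7.8), and the sponsor must act on excess adverse events (14.3.10). All true, but none of this acts on the limit in 11.4.2.

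*The radiation restriction is defensible.* Known need for adjuvant radiation is an exclusion (6.2), so few breasts should drop out, and section 9.6 treats peri-operative radiation as a confounding risk factor. This is accepted.

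A reader might also infer that the line is a binding go/no-go rule. It is not: section 11.4.2 says only that acceptable rates may support a pivotal phase. Nor is this line the reason the trial cannot show contracture to be no worse than with AlloDerm. With 25 subjects, no control arm and no hypothesis, no ceiling could show that.

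**Conclusion.** The concern holds, and its weight lies on the Grade 4 restriction. The limit does not measure the event its cited figure appears to describe, and any number of Grade II-III contractures is compatible with meeting it. That conclusion needs no assumed rates.

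The size does need them. At an assumed true rate of 24%, the limit is met with probability 0.81 to 0.92 (25 to 50 breasts) if a quarter of contractures are Grade 4, and 0.38 to 0.44 (25, 35 and 50 breasts) if half are. The result is sensitive to the Grade 4 share, which the documents do not give, so these figures are illustrations and not estimates. Calling 24% three times the benchmark also assumes that the ungraded 8% covers the same grades.

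It may be tempting to say that all three differences (grade, ceiling and radiation) materially favour the device. The documents do not support that. The ceiling changes nothing at 25 breasts and one event at 30, 35, 40 or 50, and a stated margin could justify it. The radiation restriction is minor.

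**What to change.** In section 11.4.2:

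- Define the contracture limit on the grade range counted in the review behind the 0-8% figure, and state that range. If the review does not say, use Baker Grade III-IV.
- Set the ceiling at 8%, or state the margin above 8% and its reason, for example an explicit allowance for underreporting.
- Report the rate in all reconstructed breasts beside the rate in non-irradiated breasts, and keep Grade 4 alone as a supportive summary.
- State that the limit is guidance for progression and not a test.

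No new data are needed: Baker grade is already required for the adverse event definition, and radiation status for the present limit. The cost is a limit that is harder to meet. With an 8% ceiling, a device whose true counted rate is 8% would miss it with probability of about 0.32 (25 breasts), 0.54 (35) or 0.37 (50), which is why it should not be read as a test.
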